8.3.3. Tertiary/Exploratory Analyses

The tertiary/exploratory endpoints are listed in Table 1 and will be analyzed as described below.

8.3.3.1. PRO Endpoints

8.3.3.1.1. Proportion of Subjects with $a \ge 0.5$ Decrease in ACQ-5 Score from Baseline

The proportion of subjects with a \geq 0.5 decrease from baseline in ACQ-5 score at any time postbaseline by Week 24 will be analyzed in the subset of the ITT population who have a nonmissing baseline value and at least one post-baseline value. Logistic regression modeling will be used to compare each GB001 group with placebo as for the primary endpoint. ORs, corresponding asymptotic 95% CIs along with the absolute differences and corresponding 95% CIs, and p-values will be summarized for each GB001 group versus placebo. Percentage reductions and corresponding 95% CIs will also be provided.

The number and proportion of subjects with $a \ge 0.5$ decrease from baseline in ACQ-5 score and corresponding 95% CIs will also be summarized by visit.

8.3.3.1.2. Change from Baseline in AQLQ-S

The AQLQ-S is a disease-specific, self-administered quality of life (QOL) questionnaire developed to evaluate the impact of asthma on the subject's QOL (Juniper, 1993). The questionnaire contains 32 items in 4 domains with a 2-week recall period: activity limitations (11 items), symptoms (12 items), emotional function (5 items), and environmental stimuli (4 items). Additionally, each of the 32 responses are averaged to produce an overall QOL score. Responses are scored on a seven-point scale with a value of 1 indicating total impairment and 7 indicating no impairment. The MCID is 0.5 points (Juniper, 1994).

Overall and domain scores will be derived by taking the average of the item responses at each visit. The activity limitations and symptoms domain scores will only be derived if there is ≤ 1 missing item response per domain. The emotional function and environmental stimuli domain scores will only be derived if there are no missing item responses per domain. Overall score will only be derived if all 4 domain scores are non-missing. Overall and domain scores will be summarized by visit.

Change from baseline to Week 24 in AQLQ-S will be analyzed using an ANCOVA model without MI. Covariate adjustment will be the same as for the primary endpoint except that baseline pre-bronchodilator FEV₁ will be replaced with baseline AQLQ-S. LS means will be reported along with SEs and corresponding 95% CIs, and differences between treatment groups reported with LS means, SEs, corresponding 95% CIs, and p-values. Results will be presented for the overall score only.

AQLQ-S overall and domain scores will also be presented in a by-subject data listing.

8.3.3.1.3. Change from Baseline in SNOT-22

SNOT-22 is a QOL instrument to assess the impact of chronic rhinosinusitis and utilizes a 2-week recall period (Hopkins, 2009). The questionnaire will only be completed by subjects with a prior history of sinusitis, nasal polyps, or allergic rhinitis to assess whether GB001 has an impact on this common comorbidity in patients with asthma. The questionnaire consists of 22 items across 5 domains: Nasal, Ear, Sleep, General and Practical, and Emotional. A scale ranging from 0 (no problem) to 5 (problem as bad as it can be) is used to respond to each item in the questionnaire with the total global score ranging from 0 to 110. The global MCID is 8.9.

Overall and domain scores will be derived by taking the sum of the non-missing item responses at each visit. Overall and domain scores will be summarized by visit.

Change from baseline to Week 24 in SNOT-22 will be analyzed using an ANCOVA model without MI. Covariate adjustment will be the same as for the primary endpoint except that baseline pre-bronchodilator FEV₁ will be replaced with baseline SNOT-22. LS means will be reported along with SEs and corresponding 95% CIs, and differences between treatment groups reported with LS means, SEs, corresponding 95% CIs, and p-values. Results will be presented for the overall score only.

Subgroup analyses will be performed for the following:

- Subjects with sinusitis (regardless of nasal polyps)
- Subjects with sinusitis and nasal polyps

• Subjects with sinusitis and without nasal polyps

SNOT-22 overall and domain scores will also be presented in a by-subject data listing.

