8.1.4. Asthma Control Questionnaire-5

The ACQ-5 is a five-item questionnaire which has been developed as a measure of the subject's asthma control that can be quickly and easily completed ([Juniper, 2005](#)). The questions are designed to be self-completed by the subject. The five questions enquire about the frequency and/or severity of symptoms in the prior week (nocturnal awakening, activity limitation, shortness of breath, wheeze). The response options for each of these questions consists of a zero (no impairment/limitation) to 6 (total impairment/limitation) scale. The minimal clinically important difference (MCID) is 0.5 points.

The subject should be provided with a quiet area in which to complete the questionnaire within the eDiary. The Investigator or designee should ask the subject to complete the questions as accurately as possible. If the subject requests assistance or clarification for any of the questions, he/she will be asked to reread the instructions and to select the answer that best reflects how

he/she felt over the prior week. The subject should be assured that there are no right or wrong answers. The Investigator should not provide the subject with any answer or attempt to interpret any portion of a question.

It is recommended that the ACQ be administered at the same time during each visit. To avoid biasing responses, the subject should not be told the results of diagnostic tests prior to completing the ACQ and the ACQ should be performed prior to any procedures that might influence the subject's responses. Adequate time should be allowed to complete all items on the ACQ.

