8.1.6. Sino-Nasal Outcome Test

Sino-Nasal Outcome Test (SNOT-22) is a quality of life instrument to assess the impact of chronic rhinosinusitis and utilizes a 2-week recall period (Hopkins, 2009). The questionnaire will only be completed by subjects with a prior history of sinusitis, nasal polyps, or allergic rhinitis to assess whether GB001 has an impact on this common comorbidity in patients with asthma.

The questionnaire consists of 22 items across 5 domains: Nasal, Ear, Sleep, General and Practical, and emotional. A scale ranging from 0 (no problem) to 5 (problem as bad as it can be) is used to respond to each item in the questionnaire with the total global score ranging from 0 to 110. The global MCID is 8.9.

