8.3.2.1. Change from Baseline to Week 24 Endpoints

Change from baseline to Week 24 in ACQ-5 score, pre-bronchodilator FEV₁, postbronchodilator FEV₁, and AM PEF will be analyzed as described below. The ACQ-5 is a five-item questionnaire which has been developed as a measure of the subject's asthma control that can be quickly and easily completed (Juniper E. F., 2005). The response options for each of these questions consists of a zero (no impairment/limitation) to 6 (total impairment/limitation) scale with the total score ranging from 0 to 30. ACQ-5 score is the average of the 5 non-missing items and will be calculated at each visit for each subject. The minimal clinically important difference (MCID) is 0.5 points.

For AM PEF, the baseline value is defined as the mean over the last 7 days of the Run-in including the value on Day 1 and Week 24 is defined as the mean over the last 7 days prior to Week 24 including the value on the day of the Week 24 visit. For the other endpoints, the baseline value is defined as the last non-missing value on or before the date of the first dose of study treatment.

If the number of subjects overall with a missing change from baseline value is < 5% for a particular endpoint:

- The primary analysis will be analysis of covariance (ANCOVA) without MI.
- As a sensitivity analysis, mixed-effects model with repeated measures (MMRM) without MI will also be performed.

If the number of subjects overall with a missing change from baseline value is \geq 5% for a particular endpoint:

- The primary analysis will be ANCOVA with MI.
- As sensitivity analyses, MMRM with MI, ANCOVA without MI, and MMRM without MI will also be performed.

Post-bronchodilator FEV_1 will not be analyzed using MMRM as it is collected at only one post-baseline timepoint.

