8.3.3.2. Additional Markers of Asthma Control

8.3.3.2.1. Change from Baseline in Daily Rescue Medication Use, Daily Asthma Symptom Scores, and Awakening at Night Due to Asthma Symptoms Requiring Rescue Medication Use

Rescue medications include the study-provided salbutamol/albuterol or any other short-acting bronchodilator. All rescue medication use is to be captured in an eDiary.

Change from baseline to Week 24 in daily rescue medication use, daily asthma symptoms scores, and awakening at night due to asthma symptoms requiring rescue medication use will be analyzed using an ANCOVA model without MI. Covariate adjustment is the same as the primary endpoint except that baseline pre-bronchodilator FEV₁ will be replaced with baseline rescue medication use, baseline daily symptom score, or baseline awakening at night due to asthma symptoms requiring rescue medication use, depending on the endpoint of interest.

Daily rescue medication use is collected as the number of puffs during the past 24 hours. The baseline rescue medication value is defined as the mean number of puffs over the last 7 days of the Run-in including the value on Day 1 and Week 24 is defined as the mean number of puffs over the last 7 days prior to Week 24 including the value on the day of the Week 24 visit. Similarly, the value at all other post-baseline visits is defined as the mean number of puffs over the last 7 days prior to that visit including the day of the visit.

Daily asthma symptom score over the previous 24 hours is assessed by subjects using a 6-point scale, with higher values indicating greater symptom severity, and is captured in the same eDiary as rescue medication use. Subjects also record the number of times they had awakening at night due to asthma symptoms requiring rescue medication use in this same eDiary.

Baseline and post-baseline visit values for daily symptom scores and awakening at night are defined as for daily rescue medication use. In order for the mean to be calculated at a visit, 4 out of the 7 days must have non-missing values. If < 4 of 7 days are available, the mean is considered missing.

Actual values and change from baseline values will be summarized by visit. Differences in means, SEs, and corresponding 95% CIs constructed from ANOVA models adjusting for treatment group only will also be presented. These data will also be presented in by-subject data listings.

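### SNOT-22 is scored as the sum of whatever items were answered, so a skipped item counts as the best possible response

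*SAP*

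**What the plan says.** SAP 8.3.3.1.3 describes the instrument ("The questionnaire consists of 22 items across 5 domains") and its scale ("A scale ranging from 0 (no problem) to 5 (problem as bad as it can be) is used to respond to each item"), and gives a total range of 0 to 110 and a global MCID of 8.9. The scoring rule is one sentence: "Overall and domain scores will be derived by taking the sum of the non-missing item responses at each visit". Change to Week 24 in the overall score is then analysed by ANCOVA without multiple imputation. Between-arm differences are reported with confidence intervals and p-values, and there are three subgroup analyses by sinusitis and nasal polyp status.

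Nothing else supplies a rule for blank items. Protocol 8.1.6 describes the same scale without one. SAP 8.1.1 refers missing-data handling to Section 8.3, which adds nothing at item level for this questionnaire.

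Other derived scores in the SAP are treated differently:

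- ACQ-5 (SAP 8.3.2.1): "ACQ-5 score is the average of the 5 non-missing items and will be calculated at each visit for each subject".
- AQLQ-S (SAP 8.3.3.1.2): an average. The two larger domains tolerate at most one missing item. For the other two, "The emotional function and environmental stimuli domain scores will only be derived if there are no missing item responses per domain". The overall score needs all four domains.
- Diary symptom scores and night awakenings (SAP 8.3.3.2.1): "In order for the mean to be calculated at a visit, 4 out of the 7 days must have non-missing values".

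On capture, protocol 8.1.4 says of the ACQ-5: "The subject should be provided with a quiet area in which to complete the questionnaire within the eDiary". No equivalent statement is made for SNOT-22. Protocol Appendix 12 allows SNOT-22 to be completed at home during the pandemic. Neither document says whether an item can be left blank.

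**The concern.** On a scale where 0 is the best answer, summing only the answered items is the same as imputing 0 for the rest. An incomplete form is not flagged as missing. It enters the by-visit summaries, the listings and the ANCOVA as a low, favourable score. Items skipped at Week 24 look like improvement, and items skipped at baseline look like worsening.

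The averages used for ACQ-5 and AQLQ-S do not have this property, because leaving an item out of a mean does not score it 0. The weekly AM PEF mean also has no stated minimum number of days, but it too is a mean and imputes nothing.

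Skipping that differs between visits is conceivable here. Some subjects could have an in-clinic baseline and a home Week 24 form under the pandemic provisions. Whether skipping did differ is unknown. What is at stake is one exploratory endpoint in the subset of subjects with a history of sinusitis, nasal polyps or allergic rhinitis.

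**Working it through.** **Inputs.** From the documents: 22 items, each scored 0 to 5; MCID 8.9; about 120 subjects per arm. Skip rates, item means, the item SD, the score SD, the true treatment difference and the number of SNOT-22 completers per arm are not in the documents. All values used for them below are assumptions.

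**Stated range.** 22 × 5 = 110, which matches the SAP.

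**One subject.** If *k* items of true value *v* are skipped at Week 24 only, the error in change is −*k* × *v*. Take *v* = 2 throughout, so the true total is 22 × 2 = 44 at both visits:

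- 1, 3 or 5 items skipped: −2, −6 or −10 points.
- Only one item answered: total 2, apparent change 2 − 44 = −42.
- Items needed to reach the MCID: 8.9 / 2 = 4.45, so 5. The count is 9 if each item is truly 1, 3 if truly 3 or 4, and 2 if truly 5.

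**Mean change within an arm.** Error = −22 × (Week 24 skip rate − baseline skip rate) × mean item score.

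| Baseline skip | Week 24 skip | Item mean | Error (points) |
|---|---|---|---|
| 5% | 5% | 2 | −22 × 0 × 2 = 0 |
| 2.5% | 5% | 2 | −22 × 0.025 × 2 = −1.1 |
| 0% | 5% | 2 | −22 × 0.05 × 2 = −2.2 |
| 0% | 1% | 1 | −22 × 0.01 × 1 = −0.22 |
| 0% | 10% | 3 | −22 × 0.10 × 3 = −6.6 |

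The sign reverses if the extra skipping is at baseline.

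**Added noise when skipping is equal at both visits.** Assume independent items with mean 2 and SD 1, stable true scores, and 5% skipped at each visit.

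- Complete data: variance of change 2 × 22 × 1 = 44, SD 6.63.
- Sum rule: 2 × 22 × (0.95 × 1 + 0.05 × 0.95 × 2²) = 50.2, SD 7.08.
- Prorated: approximately 2 × 22² / (22 × 0.95) = 46.3, SD 6.81.

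**Between arms, equal skipping.** The expected Week 24 score is multiplied by (1 − skip rate), and so is the difference. If 20% of Week 24 forms miss 5 items, the skip rate is 0.20 × 5 / 22 = 4.5%. An assumed true difference of −7.90 then shrinks by 7.90 × 0.045 = 0.36 points. With an assumed SD of 14.89:

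- 60 completers per arm: SE = 14.89 × √(2/60) = 2.72, and 0.36 / 2.72 = 13% of one SE.
- 120 per arm: SE = 14.89 × √(2/120) = 1.92, and 0.36 / 1.92 = 19% of one SE.

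**Between arms, unequal skipping.** Bias = difference in the share of incomplete Week 24 forms × items skipped per incomplete form × item mean.

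- 0.02 × 1 × 2 = 0.04 points
- 0.10 × 3 × 2 = 0.6 points
- 0.20 × 5 × 2 = 2.0 points

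**Check of a prorated score.** In the one-subject example with 5 items skipped, 22 × 34 / 17 = 44, so the error is 0. Proration is not exact when the worst items are the ones skipped. With two items at 5 skipped and the other 20 averaging 2, the true total is 2 × 5 + 20 × 2 = 50. The sum rule gives 40 (error −10) and proration gives 22 × 2 = 44 (error −6).

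**The case against.** The strongest reply is that the harm is hypothetical. The documents give no skip rate, and an electronic form may not allow blanks, in which case the error is zero. The between-arm comparison is also robust: the trial is double-blind, nothing suggests that skipping would differ by arm, and equal skipping only attenuates the difference slightly. The larger figures above (−2.2 and −6.6) are errors in single-arm mean change with no skipping at baseline, and should not be read as errors in the treatment effect. All of this stands, and it limits the importance of the point.

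Two further points are fair. The ACQ-5 sentence can be read as requiring all five items or as averaging whatever was answered, so AQLQ-S is the only questionnaire with a clear item-level minimum. And a threshold of half the items is a choice that the documents do not dictate; it is looser than the SAP's own AQLQ-S rule.

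None of this repairs the rule. By referring to non-missing responses it provides for blanks, and it then scores them as the best answer. On either reading of the ACQ-5 sentence, an average does not do that.

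**Conclusion.** The rule is wrong as written, at minor severity. It misstates an incomplete form by the true value of every skipped item, which for one subject can exceed the MCID. At group level, under the assumed rates and item means:

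- Error in mean change runs from 0 with equal skipping to between 0.2 and 6.6 points when items are skipped at only one of the two visits.
- Between arms, equal skipping attenuates the difference by about the Week 24 skip rate.
- Between arms, unequal skipping gives bias of 0.04 to 2.0 points over the range shown.
- If capture prevents blanks, every one of these is zero.

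Confidence is high that the rule mis-scores incomplete forms. Whether it matters in practice cannot be judged from the documents. Primary and secondary conclusions are unaffected.

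**What to change.** Replace the scoring sentence in SAP 8.3.3.1.3 with a rule such as:

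> If at least 12 of the 22 items are answered, the total is 22 times the mean of the answered items; otherwise the total is missing. Each domain score is the number of items in that domain times the mean of its answered items if more than half are answered; otherwise it is missing.

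The threshold of 12 is one option. A stricter minimum in the spirit of the AQLQ-S rule would also do, provided it is fixed before the unblinding for the interim analysis. The number of items per domain should be written in, since neither document gives it. If the capture system requires every item to be answered, a sentence saying so is enough and no scoring change is needed.

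The cost is one SAP sentence and one line of derivation code. Complete forms score exactly as now. Forms with too few answers become missing, but if items are skipped at random very few fall below 12 answered: the binomial probability of at least 11 of 22 skipped is 2.5 in a million at a 10% skip rate and 0.16% at 20%. In practice the loss is confined to abandoned forms. Some error remains if subjects tend to skip their worst items.

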8.3.3.1.4. Change from Baseline in Hair-Loss Assessment

A visual scale (Norwood classification for male subjects and Savin classification for female subjects) to characterize the degree of scalp hair loss at baseline and at the end of the study will be used (Gupta, 2016). This information will be complemented with a modified questionnaire to assess patient perceptions of scalp hair growth at the end of the study. This questionnaire includes 2 simple questions to describe possible scalp hair growth changes during the study period.

Cross tabulations of the Baseline assessment versus the Week 24 assessment will be presented for the Norwood classification for males and Savin classification for females separately.

Hair-loss assessment data will also be presented in a by-subject data listing.

8.3.3.2. Additional Markers of Asthma Control

8.3.3.2.1. Change from Baseline in Daily Rescue Medication Use, Daily Asthma Symptom Scores, and Awakening at Night Due to Asthma Symptoms Requiring Rescue Medication Use

Rescue medications include the study-provided salbutamol/albuterol or any other short-acting bronchodilator. All rescue medication use is to be captured in an eDiary.

Change from baseline to Week 24 in daily rescue medication use, daily asthma symptoms scores, and awakening at night due to asthma symptoms requiring rescue medication use will be analyzed using an ANCOVA model without MI. Covariate adjustment is the same as the primary endpoint except that baseline pre-bronchodilator FEV₁ will be replaced with baseline rescue medication use, baseline daily symptom score, or baseline awakening at night due to asthma symptoms requiring rescue medication use, depending on the endpoint of interest.

Daily rescue medication use is collected as the number of puffs during the past 24 hours. The baseline rescue medication value is defined as the mean number of puffs over the last 7 days of the Run-in including the value on Day 1 and Week 24 is defined as the mean number of puffs over the last 7 days prior to Week 24 including the value on the day of the Week 24 visit. Similarly, the value at all other post-baseline visits is defined as the mean number of puffs over the last 7 days prior to that visit including the day of the visit.

Daily asthma symptom score over the previous 24 hours is assessed by subjects using a 6-point scale, with higher values indicating greater symptom severity, and is captured in the same eDiary as rescue medication use. Subjects also record the number of times they had awakening at night due to asthma symptoms requiring rescue medication use in this same eDiary.

Baseline and post-baseline visit values for daily symptom scores and awakening at night are defined as for daily rescue medication use. In order for the mean to be calculated at a visit, 4 out of the 7 days must have non-missing values. If < 4 of 7 days are available, the mean is considered missing.

Actual values and change from baseline values will be summarized by visit. Differences in means, SEs, and corresponding 95% CIs constructed from ANOVA models adjusting for treatment group only will also be presented. These data will also be presented in by-subject data listings.

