8.1. Efficacy Assessments

8.1.1. Asthma Worsening (Primary Endpoint)

At each visit, the Investigator or designee will:

- Download and review the eDiary report for alerts for AM PEF, rescue medication use, and asthma symptoms
- Have the subject complete the ACQ-5 in clinic and review to assess for an increase in ACQ-5 score ≥ 0.5 compared to baseline
- Measure spirometry at each visit except Visit 3 (Week 2), and the FEV₁ will be assessed to look for a decrease of $> 20\%$ from baseline
- Interview the subject to inquire about recent use of systemic corticosteroids (for 3 or more days) for asthma, or an Emergency Department visit or hospitalization for asthma. If the criteria for a severe asthma exacerbation are met, the site staff will complete the exacerbation page within the eCRF. Courses of systemic corticosteroids separated by 7 or more days will be counted as separate severe exacerbations.

8.1.2. eDiary Asthma Parameters and Alerts

The subject will be asked to record the following parameters daily in the eDiary from the Screening visit through the Follow-up visit:

- Morning peak flow (best of three efforts) before rescue medication usage (L/min)
- Puffs of rescue medication used over the previous 24 hours
- Asthma symptom score over the previous 24-hours using a 6-point scale (Appendix 7 in [Section 10.7](#))

- Frequency of awakening due to asthma symptoms requiring rescue medication use

The eDiary is programmed to alert the subject about potential asthma worsening. Please refer to [Section 4.1.1](#) for alert criteria.

Subjects will be issued a paper worksheet to record new medical problems and medications taken during the study. This will be used to assist subject recall in discussions with the Investigator or designee.

The eDiary information is to be downloaded and reviewed at each visit for potential asthma worsening, asthma exacerbations, and to assess compliance with eDiary completion. The subject diary data should be archived by site at the end of the study.

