2.5. Sample Size Determination

A total sample size of approximately 480 subjects (approximately 120 per treatment group, randomized in a 1:1:1:1 ratio) is estimated to provide 80% power to detect a reduction in odds of 66% between each GB001 group and placebo at an 0.050 two-sided level of significance for the primary endpoint of the proportion of subjects who experience worsening of asthma by Week 24. This assumes the proportion of subjects who experience worsening of asthma by Week 24 is 25% in the placebo group and 10.2% in each GB001 group and a dropout rate of 8%.

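### The adjusted Week 24 comparison of three exploratory eDiary endpoints is complete-case with no missing-data sensitivity analysis, so it may be biased, in an unknown direction, if dropout tracks asthma control

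*SAP*

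**What the plan says.** SAP 8.3.3.2.1 covers daily rescue use, daily symptom score and night awakening needing rescue. The last of these, like the other two, "awakening at night due to asthma symptoms requiring rescue medication use will be analyzed using an ANCOVA model without MI". For rescue use, "Week 24 is defined as the mean number of puffs over the last 7 days prior to Week 24", with the visit day included, and the other two endpoints follow the same definition. On incomplete weeks the rule is "If < 4 of 7 days are available, the mean is considered missing". SAP Table 1 (section 8.2) marks each endpoint once, as a primary analysis under ANCOVA without MI, and lists no sensitivity analysis.

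The same section also derives values at earlier visits: "the value at all other post-baseline visits is defined as the mean number of puffs over the last 7 days prior to that visit". These are summarized by visit, and "Differences in means, SEs, and corresponding 95% CIs constructed from ANOVA models adjusting for treatment group only will also be presented".

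AM PEF comes from the same eDiary and is also a 7-day mean, but it is a secondary endpoint. For it, SAP 8.3.2.1 sets a rule by amount missing. At 5% or more, "The primary analysis will be ANCOVA with MI", with MMRM (with and without MI) and ANCOVA without MI as sensitivity analyses. Below 5%, ANCOVA without MI is primary and MMRM is the sensitivity analysis.

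On data collection, Protocol 8.1.2 says: "The subject will be asked to record the following parameters daily in the eDiary from the Screening visit through the Follow-up visit". Protocol 4.1.1 and 7.1 encourage subjects who stop IP to remain and complete their visits.

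**The concern.** The stated aim is the effect of GB001 on markers of asthma control, and SAP 8.2 assigns efficacy results to the ITT population unless otherwise stated. The adjusted model instead estimates the effect among subjects who still supply a diary week at Week 24. Someone who withdraws at Week 16 contributes nothing to it, although their 7-day means up to that point have already been derived.

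Complete-case ANCOVA is unbiased when missingness depends only on treatment and the baseline covariates. It can be biased when missingness also depends on how the subject was doing after randomization, and rescue use, symptoms and awakenings measure exactly that. Protocol 7.2 lists lack of efficacy among the reasons for withdrawal. SAP 3.3 anticipates withdrawals, missed visits and lost eDiary data during the pandemic, while its non-exhaustive examples of extra efficacy analyses name only the primary and select secondary endpoints.

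At stake is how these endpoints are read. If they disagree with AM PEF or ACQ-5, nothing planned would show whether missing data explain the difference.

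**Working it through.** **Inputs from the documents.** Worsening 25% on placebo and 10.2% on each GB001 dose; dropout 8%, not split by arm or reason; about 120 per arm and 480 in all (SAP 2.5); 5% threshold for AM PEF (SAP 8.3.2.1). **Not in the documents, so assumed:** SD, effect size and dropout by arm for the diary endpoints.

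**1. The plan's own figure.** Odds ratio = (0.102/0.898)/(0.25/0.75) = 0.341, a 66% reduction. Evaluable per arm = 120 × 0.92 = 110.4. SE of the log odds ratio = √[1/(110.4×0.25×0.75) + 1/(110.4×0.102×0.898)] = 0.384. Power = Φ(1.077/0.384 − 1.96) = 0.80. The stated 80% is reproduced. It concerns the primary endpoint; no power is stated for the diary endpoints.

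**2. How many are left out.** If every dropout lacks a Week 24 mean, 0.08 × 480 = 38.4 subjects are missing, against the AM PEF threshold of 0.05 × 480 = 24. On the plan's own assumption, AM PEF would therefore fall under the MI branch. The 4-of-7 rule can add further missing values. The loss of precision is small: for an assumed 0.30 SD effect, Φ(0.30/√(2/n) − 1.96) falls from 0.64 at n = 120 to 0.61 at n = 110.4.

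**3. Direction of bias.** Simulation with 200,000 per arm, assumed true effect −0.30 SD (lower is better), and correlations of 0.6 (baseline–mid-study), 0.5 (baseline–Week 24) and 0.7 (mid-study–Week 24). Dropout is either unrelated to outcome or more likely with a worse mid-study score. The last column imputes Week 24 within arm from baseline and the mid-study value.

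| Dropout scenario | Full data | Complete-case | Using earlier visit |
|---|---|---|---|
| 8% both arms, unrelated | −0.300 | −0.300 | −0.300 |
| 8% both arms, worse subjects leave | −0.298 | −0.299 | −0.299 |
| Placebo 12%, active 4%, worse leave | −0.295 | −0.265 | −0.294 |
| Placebo 12%, active 6.7%, worse leave | −0.298 | −0.279 | −0.298 |
| Placebo 8% worse leave, active 8% unrelated | −0.296 | −0.265 | −0.295 |
| Placebo 4%, active 12%, worse leave | −0.300 | −0.326 | −0.298 |
| Placebo 4%, active 9.3%, worse leave | −0.294 | −0.312 | −0.293 |
| Placebo 8% unrelated, active 8% worse leave | −0.298 | −0.329 | −0.298 |

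The extremes are 0.031/0.296 = 10% understated and 0.031/0.298 = 10% overstated. With residual SD √(1 − 0.5²) = 0.866, the SE of the contrast is 0.866 × √(2/110.4) = 0.117 SD. A bias of 0.031 is therefore about a quarter of an SE.

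**4. How far earlier visits help.** In step 3 dropout depends on an observed value, so missing-at-random holds by construction and recovery is nearly complete. A harsher simulation used 7 visits, 120 per arm, correlation 0.6 and a 1 to 2 SD shift after worsening, with a share g of all withdrawals following worsening. Complete-case bias was about −8%, −18% and −38% at g = 25%, 50% and 100%. A likelihood analysis of all visits reduced it to −4 to −5%, −9 to −11% and −20 to −25%. That removes between 1 − 25/38 = 34% and 1 − 4/8 = 50% of the bias, with an SE no larger to within about 1%.

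**The case against.** **Tiering.** AM PEF is secondary and these endpoints are tertiary/exploratory. Table 1 gives the modelled continuous tertiary endpoints ANCOVA without MI throughout. That is a choice by importance, so a reader who infers an internal contradiction goes too far. What remains is that sparse data cannot justify the simpler method here: AQLQ-S and SNOT-22 have Week 24 as their only scheduled on-treatment post-baseline visit, whereas these endpoints have values at every visit.

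**Earlier diary data are used.** A reader might infer that the arms are compared only among subjects with a Week 24 diary week. The by-visit ANOVA differences show otherwise. They are unadjusted and use whoever is observed at each visit, so they leave the Week 24 contrast as it is.

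**Fewer subjects are lost than it seems.** Stopping IP is not withdrawal, and such subjects can still supply a Week 24 week. A late withdrawal visit may also fall in the Week 24 window, which under SAP 3.1 starts at the midpoint of Days 141 and 169, Day 155. This narrows the affected group but does not empty it.

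**Understatement is not established.** A reader might infer that the effect is understated, by tying withdrawals to the 25% and 10.2% worsening rates. With mean worsening (0.25 + 3 × 0.102)/4 = 0.139, a fraction a = 0.08g/0.139 of worsened subjects leaving, and p(1 − a)/(1 − pa) worsened among those who remain, the difference shrinks by 10%, 21% and 47% at g = 25%, 50% and 100%. The documents do not give g. At g = 100% this needs 0.08/0.139 = 58% of worsened subjects to leave. It also assumes that the whole marker difference arises through worsening. Worsening is not a mandatory stopping criterion, SOC may be adjusted after it (Protocol 6.4), and SAP Table 2 concerns subjects who withdraw without having worsened. Adverse-event withdrawals on GB001, where liver injury is a named potential risk (Protocol 2.3.1), could give no bias or the opposite bias.

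**Conclusion.** The point holds in limited form. The adjusted Week 24 ANCOVA for the three eDiary endpoints omits subjects without a Week 24 diary week, makes no use of their earlier values, and has no planned missing-data sensitivity analysis. If dropout is related to asthma control, the contrast may be biased: toward the null if poorly controlled placebo subjects leave more often, otherwise not at all or in the other direction.

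The size cannot be derived from the documents. Under the assumptions of step 3 it ranges from zero to about 10% either way, roughly a quarter of an SE. The larger one-sided figures depend on an unstated share of withdrawals following worsening and should not be quoted as the expected bias. The consequence is low, since neither the primary nor the secondary endpoints are affected.

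**What to change.** In SAP 8.3.3.2.1 and Table 1, apply the AM PEF rule of SAP 8.3.2.1 to these three endpoints, using the 7-day means already derived at each visit:

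- **5% or more missing a change to Week 24:** ANCOVA with MI primary; MMRM (with and without MI) and ANCOVA without MI as sensitivity analyses.
- **Under 5%:** ANCOVA without MI primary; MMRM as sensitivity analysis.

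Keep baseline ACQ-5 as a covariate. The current ANCOVA includes it, but the MMRM in 8.3.2.1 does not list it. State that the imputation model includes the earlier 7-day means. At minimum, pre-specify the MMRM as a sensitivity analysis; SAP section 1 says that analyses added beyond the plan will be labelled post hoc.

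The cost is a change of wording and a few more runs of programs already specified. The result would rest on a missing-at-random assumption, which is weaker than what complete-case ANCOVA requires. It would not remove all bias if subjects leave because of deterioration that the diary means have not yet captured.
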